# DECIDE Parent-Provider Interaction IRB Protocol

## 1.0 Rationale

Interventions to optimize parent-provider interactions are urgently needed to ensure adolescents with Disruptive, Impulse-Control, and Conduct disorders (DIC) receive the behavioral health care they need. DIC affect 5 million (1 in 5) American adolescents aged 12 to 17 years. DIC are characterized by emotional and behavioral dysregulation manifested by behaviors that are aggressive, infringe on the rights of others, violate social norms, and result in conflicts with authority figures. For these adolescents, behavioral health care is complex, long-term, and requires parental participation. Research by our team and others showed parents of these adolescents report that providers do not listen to them or involve them in their adolescents' care. Research shows providers have biases and limited skills and confidence to communicate with these parents to encourage them to voice their concerns and care preferences. Low income and/or minority parents are at greatest risk for not being involved in their adolescents' behavioral health care, having poor interactions with providers, being more likely to perceive poor quality of their adolescents' behavioral health care, and having low treatment engagement. If unaddressed, poor parent-provider interactions interfere with adolescents' retention in behavioral health care. No evidence-based interventions have targeted both parents and providers to optimize their interactions and improve behavioral health care for adolescents with DIC.

To address these problems, we propose modifying the evidence-based DECIDE intervention to target low income and/or minority parents and providers of adolescents with DIC. DECIDE stands for Decide the problem; Explore the questions; Closed or open-ended questions; Identify the who, why, or how of the problem; Direct questions to your health care professional; Enjoy a shared solution. DECIDE was developed for ethnically/racially diverse adult patients with serious mental illness, and the latest evidence-based iterations include intervention components targeted to and shown to increase patient activation, provider communication, and patient-provider interactions. DECIDE has two primary components: 1) three patient training sessions designed to help patients effectively ask questions and participate in decisions about care; and 2) a 12-hour workshop and up to 4 individual coaching sessions for providers to improve perspective-taking, reduce attributional errors, and increase receptivity to patient participation. DECIDE has improved patient activation, self-management, perceived quality of care, and collaborative treatment decision making.

## 2.0 Background

**Adolescents with disruptive, impulse-control, and conduct disorders (DIC), especially those in low income and/or minority families, present some of the nation's most pressing behavioral health care challenges.** Five million (1 in 5) adolescents 12-17 years of age are diagnosed with a DIC that includes the following DSM-5 diagnoses: (a) Oppositional Defiant Disorder, (b) Conduct Disorder, (c) Intermittent Explosive Disorder, (d) Pyromania, (e) Kleptomania, (f) Other Specified DIC Disorder, and (g) Unspecified DIC. DIC are characterized by emotional and behavioral dysregulation manifested in externalizing behaviors that are aggressive, infringe on the rights of others, violate social norms, and result in conflicts with authority figures. Annual medical costs average \$14,000 per child with Conduct Disorder compared to < \$2300 per child without a mental disorder. Annual direct medical costs range from \$17 to 56 billion for those with DIC. Parents incur financial costs associated with interruptions in employment due to caregiving responsibilities, increased healthcare needs for their own stress-related illnesses, and their child's treatment. Approximately 57% of children with mental health disorders, including DIC, come from households living at or below the federal poverty level, and low income and/or minority parents are particularly vulnerable to the negative effects of caregiving for adolescents with these

## DECIDE Parent-Provider Interaction IRB Protocol

disorders. Problems associated with DIC are exacerbated during adolescence due to rapid developmental changes and increased substance abuse and criminal activities.

**The effective treatment of adolescents with DIC depends on their parents' active engagement with behavioral health care providers.** In addition to managing their adolescents' problem behaviors and their own distress over such behaviors, parents of adolescents with DIC must attend frequent and often urgent meetings with providers. Active parent involvement with the mental health system is required due to the complex treatment regimens needed by adolescents with these disorders and the high-risk nature of their behaviors. Parents report that encounters with providers are often time-consuming, stressful, stigmatizing, exhausting, and unhelpful. Negative interactions with providers contribute to parent disengagement from their adolescents' care and resistance to following provider recommendations, both of which lead to poor adolescent outcomes.

**Low income and/or minority parents of adolescents with DIC are at high risk for aversive interactions with providers due to socioeconomic disadvantages.** Research has shown that effective communication skills deployed by consumers in healthcare encounters, such as asking informed questions and clearly articulating opinions and needs, are associated with greater satisfaction with care and better health outcomes. However, low income and/or minority persons often have less opportunity to acquire these skills due to low educational attainment, poor health literacy, disadvantaged social position, and limited resources. Negative interactions are fostered by providers who perceive low income and/or minority health consumers to be uninvolved, uninformed, and unable to make complex health care decisions, and lack of training about how to motivate low income and/or minority persons to voice treatment concerns and preferences.

**Scientific Premise: To address the above issues, research suggests appropriate target variables for parents and providers are parent activation, provider communication, and parent-provider interactions.** Activation is a person's acquisition of knowledge, skills, and beliefs that facilitate active participation in health care. High activation in adult patients with chronic illness, such as diabetes, HIV/AIDS, hypertension, and serious mental illness such as schizophrenia is associated with better health status and adherence to healthy behaviors. Consumers who are well informed about health conditions and who are confident in their abilities to navigate the healthcare system and manage their care have better health outcomes. In addition, improving provider communication increases satisfaction, adherence, and health outcomes in pediatric and adult populations with physical and mental health concerns. Multiple factors contribute to the quality of patient-provider interaction including provider communication and institutional practices. Effective provider communication is characterized by attentive, facilitative, and collaborative behaviors.

Benefits of parent interventions will not be fully realized without collaborative parent-provider interactions. Several parent support and skills training interventions have been shown to improve: 1) parent knowledge and management of their children and adolescents' behavior problems, 2) parent mental health and stress levels, and 3) parent self-efficacy in accessing and navigating adolescents' mental health services. Moreover, activation interventions in adult behavioral health have demonstrated that patient activation in the absence of provider support can lead to harmful effects, including further exacerbation of tension in patient-provider relationships or diminished patient use of services particularly in low income and/or minority patients. Patients' perception or belief that the provider is supportive (receptive) of the former's efforts to be actively involved in treatment may act as a mediator of intervention effects. Alegria and colleagues suggested that patients' beliefs that providers will support their activation efforts may significantly contribute to benefits of patient-provider interactions, patient perception of management of care, perceived quality of care, and engagement and retention in care.

**Our proposed focus on both parents and providers is innovative in this field.** In DIC and other mental health disorders, there are several support programs or interventions targeting parents. However, there are no (zero) interventions targeting providers, and no interventions targeting both parents and providers. This was confirmed in a PubMed search of all existing English-language literature using terms "parent, mental health, activation or empowerment, and intervention".

## DECIDE Parent-Provider Interaction IRB Protocol

**Our target variables are innovative in this field.** Improving parent activation improves interactions with providers yet only two studies to date have tested parent activation interventions in adolescent behavioral health care. These two studies showed positive effects on parent activation and perceived efficacy to work with mental health providers. However, neither study intervened with providers. Similarly, improving provider communication increases satisfaction, adherence, and health outcomes. Yet there are no such existing interventions for parents of children with DIC. This was confirmed in a PubMed search of all existing English-language literature using terms “parent - provider communication, mental health, and intervention. Provider communication interventions have been developed to improve encounters between healthcare providers and adult patients with physical health concerns, and parents of children in pediatric primary care. However, evidence-based parent-provider communication interventions for parents of children with mental health disorders, including DIC, have not been developed. Thus, this is the first intervention to improve interactions between parents and providers of adolescents with DIC.

**Our inclusion of low income and/or minority parents addresses an understudied population.** The existing parent activation intervention studies focused on military families or Latino parents. The military sample was majority white (73%) and middle income. Our study will include a more racial/ethnic diverse sample.

### **3.0 Specific Aims**

The **purposes** of this two-phase study are to modify and test the DECIDE intervention (referred to as DECIDE from now on) for parents and providers of adolescents with DIC. In phase I, our team in Indianapolis, IN (Drs. [name], [name], [name], parent and provider advisory boards) will work with two consultants to modify DECIDE. [name] will help modify the DECIDE provider components to be relevant for DIC. [name] will help modify DECIDE from patient to parent focused. In phase II, we will test modified DECIDE against usual care in parents and providers of adolescents with DIC using a two-group, pilot, randomized, controlled design. During phase II, [name] became a Co-Investigator at the University of South Florida in Tampa, FL. [name] (New York, NY) has clinical expertise in improving activation among parents of adolescents with DIC. [name] (Northampton, MA) led the design and implementation of DECIDE components targeted to providers [name] will help modify DECIDE from patient to parent focused. Our setting is a large, safety net health system in the Indianapolis metropolitan area servicing primarily low income and/or minority persons.

**Specific aims** are to:

**Phase I, Aim 1.** Modify DECIDE for low income and/or minority parents and providers of adolescents with DIC.

**Phase II, Aim 2.** Evaluate the feasibility and acceptability of modified DECIDE.

**Phase II, Aim 3.** Estimate preliminary effects of modified DECIDE to improve parent, provider, and adolescent outcomes. We hypothesize that compared to usual care:

**Hypothesis 3.1.** Modified DECIDE parents will show greater improvements in: 1) activation; 2) parent-provider interactions; 3) perceived management of adolescents' behavioral health care, 4) perceived quality of adolescents' behavioral health care, and 5) engagement in adolescents' behavioral health care.

**Hypothesis 3.2.** Modified DECIDE providers will show greater improvements in: 1) communication skills and 2) parent-provider interactions.

**Hypothesis 3.3.** Adolescents of modified DECIDE parents and providers will show higher rates of retention in behavioral health care.

If study findings are positive, we will be poised to test the modified DECIDE in a fully-powered R01 level randomized, controlled, multi-site clinical trial. If study findings are negative, we will have process and outcome information needed to further refine DECIDE or pursue different interventions. Either way, this line of research has potential to optimize parent-provider interactions and ultimately, ensure adolescents with DIC receive the behavioral health care they need.

## DECIDE Parent-Provider Interaction IRB Protocol

### **4.0 Inclusion/Exclusion Criteria**

#### **Inclusion Criteria:**

Inclusion Criteria for providers and interns: Providers will be regular paid staff members who are:

- (1) Associate's or bachelor's or PhD prepared providers who work with parents **OR**
- (2) Masters-prepared clinical social workers or mental health counselors **and**
- (3) Provide behavioral health services to adolescents and their parents. **OR**
- (4) Doctoral level interns (e.g. in psychology) **and**
- (5) Provide behavioral health services to adolescents and their parents **OR**
- (6) Providers who are bachelor's prepared interns must:
  - (1) be currently working with a center or private practice to complete requirements for their Master's degree **and**
  - (2) be providing behavioral health services to adolescents and their parents.

Inclusion Criteria for Guardians: Guardians will have a child or adolescent with DIC receiving services from a participating mental health provider. Parents/guardians meeting all the following criteria are eligible:

- (a) are aged 21 or older
- (b) speak English
- (c) are the guardian (biological parent, adoptive parent, step parent, foster parent, or legal guardian) of the child or adolescent or a parent surrogate serving in a primary caregiver role (referred to as "parents"; if foster parent or legal guardian, ).
- (d) must have a child or adolescent aged 3 to 17 years with a diagnosis of Disruptive Impulse Control and Conduct Disorder (DIC) by a mental health professional. (This includes children with behavior problems, such as Oppositional Defiant disorder, Conduct disorders, or Intermittent Explosive disorders).
- (e) Attends regular appointments with a provider
- (f) Foster parents will be included if they have a child with DIC now or in the past, and regardless of whether that child is receiving services from a participating mental health provider or not.

#### **Exclusion Criteria for parents:**

- Show significant cognitive impairment or acute emotional distress on screening
- Have an incarcerated adolescent

No providers or parents will be excluded on basis of race/ethnicity, gender, or sexual orientation.

### **5.0 Enrollment/Randomization**

#### **Screening**

Providers currently employed at Sandra Eskenazi Mental Health Hospital, Bowen Center, Centerstone, and other applicable mental health centers or private practice will be approached for inclusion on the study. Providers with at least one patient who is aged between 6-17 and diagnosed with DIC disorders will be screened for enrollment.

#### **Informed Consent**

A study investigator or research assistant will obtain informed consent from the provider either via a HIPPA compliant teleconferencing platform (ie Zoom Health) or via telephone contact. Parents who become

## DECIDE Parent-Provider Interaction IRB Protocol

enrolled will be approached via telephone contact. Informed consent for parents will be obtained virtually via a HIPPA compliant teleconferencing platform (i.e., Zoom Health) or telephone contact.

### **Randomization**

All participants will be assigned to the intervention arm and there will be no randomization. Instead, the intervention results will be compared to historical data.

### **Study Duration/Timeline**

The study will consist of the provider completing baseline measures and then complete a 4.5 hours (max) workshop through Canvas Learning System, completed over the course of 2-3 weeks. After the provider completes the workshop, he/she will be contacted by study staff to complete the post-intervention measures (T2) and conduct a recorded qualitative interview. The parents will complete baseline (T1) study measures before meeting with the parent trainer. Then all will participate in up to three, hour-long sessions training sessions with a parent trainer. In total, participation in the study will last between 6-8 weeks.

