### **3. Methods**

## DECIDE Parent-Provider Interaction IRB Protocol

**DECIDE Intervention.** The evidence-based DECIDE intervention was developed for low income and/or minority adults with serious mental illness and their providers. DECIDE has both patient and provider components. DECIDE has improved patient activation, patient self-management, perceived quality of care, and improved collaborative treatment decision making. Because DECIDE was designed for individuals who work with adult patients, we will adapt it for parents and providers of adolescents with DIC. For example, case examples need to be relevant to the clinical work with this population and accommodate individual or family therapy; we will also shorten the provider training – to increase feasibility of implementation and acceptability to participants. This fits with Stage 1A and 1B of the ORBIT model.

The **modified DECIDE** will have parent and provider components.

The **parent component** is designed to teach parents how to effectively ask questions and participate in decisions about their adolescents' behavioral health care. It will include up to three 60 minutes sessions (the third session is optional). Session 1 (Decisions and Agency) is designed to increase awareness of their role in clinical interactions and encourage participation and decision making in care. Session 2 (Self-efficacy and Consolidation) encourages parents to ask questions about their adolescents' behavioral health and health care and treatment options . Session 3(Optional Booster), which can discuss any previous topics the parent would like the trainer to review and can also include more practicing of asking questions).

The **provider component** is designed to improve provider communication in three key areas: 1) perspective taking to understand circumstances and perceptions; 2) attributional errors or attributing negative parent behaviors to character traits instead of considering the situational factors; and 3) receptivity to parent participation and collaboration. We will shorten the provider training to increase feasibility of implementation and acceptability to participants. The training will included one 4.5-hour (rather than 12-hour) group workshop.

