#### Revised Study Schema:

Figure 2: Study Schema							
Providers	Recruitment	Screening	Consent	Baseline	Modified DECIDE intervention [workshop ([contact] hrs)]	Time 2	DECIDE Oral Interview (all providers)

**DECIDE Parent-Provider Interaction  
IRB Protocol**

Parents	Recruitment	Screening	Consent	Baseline	Modified DECIDE sessions 2 @ 1 hr/week, with an optional 3 rd booster session offered @ 1 hr/week	Time 2	DECIDE Oral Interview (subset of parents)
Green: Quantitative measures and oral interviews							
All participants will receive the DECIDE intervention. Results will be compared to historical control.							

Training for parents will be delivered remotely using telephone and/or Zoom Health for parents with video capability. The parents will be sent a Zoom Health invitation which include a toll free number they can call. This allows research staff to record sessions for fidelity checks.

**Data collection.** A trained study staff will collect baseline data (T1) before the provider takes the DECIDE Training and will schedule a follow-up assessment 1- 4 weeks post intervention training (T2). Providers will be instructed to think specifically about the most recent therapy session that he/she had with a parent of a child diagnosed with DIC in order to keep the parent provider interaction fresh in the provider's mind when completing the measures. Study staff will follow these same guidelines for scheduling the T2 data collection. Providers will complete and enter their surveys directly into REDCap. Providers will be contacted by study staff to remind them to complete their surveys and to answer any questions if necessary. Study staff will schedule an appointment with providers to collect the post-intervention (T2) measures in order to ensure the provider understands the instructions and also to conduct the post-intervention qualitative interview. Providers will be instructed to think specifically about the most recent therapy session that he/she had with a parent of a child diagnosed with DIC in order to keep the parent provider interaction fresh in the provider's mind when completing the measures. Parents will be contacted and asked to schedule a convenient time to complete the surveys with the study staff.

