**Measures.**

**Aim 2 measures.** The research project coordinator will keep logs and field notes of feasibility including: 1) enrollment rates, reasons for ineligibility and declining participation; 2) attrition rate, reasons for missed session or intervention completion; and (3) measurement completion rates. We will measure parent and provider acceptability and satisfaction with modified DECIDE using Client Satisfaction Questionnaire (CSQ) and in-depth semi structured interviews at T2. RAs under [name]'s supervision will conduct in-depth semi-structured interviews including: All intervention providers (n = 8) and two of each of the parents (n = 16). To explore different levels of acceptability by parents, for each provider, one parent will be chosen who has a high score (> 3) on the CSQ and one parent who has a low score (< 3). Both parents and providers will be asked about their experience with the intervention, what was helpful or not, and how they would change the intervention.

**Aim 3 measures.** Parents, providers, and adolescents' socio-demographic factors will be assessed at T1; and outcomes will be assessed at T1 and T2. We will include three items (i.e., level of parent organization, involvement, and management of adolescents' care) from the Child and Adolescent Needs and Strengths (CANS) at Midtown's request. We will use self-administered questionnaires with read-aloud procedures to address issues of literacy. All measures have well-established psychometric properties, sensitivity to change, and acceptable response burden. Multi-informant and mixed methods assessment of outcomes is a study strength. Given the change in design to one group pre and post intervention compared to historical group; we will use the Parent Participation Engagement Measure (PPEM). In lieu of Working Alliance Inventory or Kim Alliance Scale as our key measure of parent-provider interaction or engagement.

**DECIDE Parent-Provider Interaction  
IRB Protocol**

Table 1: Measures					
Variables	Measure	#Items	Reliability (<math>\alpha</math>)	Schedule	Filled By
Antecedents					
Parent Factors	Parent Information Form	10	N/A	T1	Parent
Provider Factors	Provider Information Form	10	N/A	T1	Provider
Adolescent Factors	Adolescent Information Form	7	N/A	T1	Parent
Feasibility/Acceptability					
% Eligible participants enrolled	Investigator Tracking Logs	N/A	N/A	T2	PI

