*Safety.* The committee will monitor adverse events reported by participants and reasons for dropping out. Adverse events will be reported to the study PI or her designee within 24 hours, and any serious unexpected adverse events related to the study intervention will be reported to the Institutional Review Board within 5 working days. The relationship between adverse events and the study intervention will be determined based on PI and her research staff examination of the subject (research staff and/or patient) and subsequent clinical judgment. Both provider and parent participants will have several phone numbers to call should they have any concerns or questions about any aspect of the study, including contact numbers for the PI, the project coordinator, the IRB offices, and the parent/patient representatives at Midtown. All other adverse events will be reported annually with the continuing review. Study Withdrawal/Discontinuation. Taking part in the study is voluntary. A participant may choose not to take part in the study or to withdraw from the study at any time. If the participant withdraws from the study, he/she will not be penalized in any way and will not lose any benefits he/she is entitled. The participant may choose to contact the study PI to formally withdraw, or he/she may simply choose to stop coming to the study sessions. If the participant chooses to withdraw, a study representative will call the participant to make sure he/she is ok. The study representative will provide the participant with contact numbers to obtain other resources. For example, parents may be provided number to other Midtown programs or National Alliance on Mental Illness (NAMI) Indianapolis. In addition, the PI will meet monthly with the research project coordinator to review data collected to date in order to determine if there are any major problems in data collection procedures or data collected.

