### **9.0 Statistical Considerations**

We will calculate the proportion eligible that enroll and proportion completing the intervention for both parents and providers. We will tabulate responses to Parent and Provider Satisfaction with Intervention items and calculate the proportion of parents and providers who have a mean ratings of at least 4 on the 5-point scale (satisfied or highly satisfied). Effect sizes will be estimated by fitting linear mixed models, with parent, provider, or observer target and outcomes variables, all measured at T2, as outcomes and treatment group (intervention or usual care) as the explanatory variable. All models will also include the T1 outcome as a covariate and random effects for provider and parent nested within provider to account for clustering. Effects sizes will be estimated with  $\omega^2$ . Analyses will be intent-to-treat and conducted using SAS Version 9.4 (SAS Institute Inc., Cary, N.C., Copyright 2002-2012).

*Supplementary Analyses:* We will investigate how the adjustment for covariates (age of child, sex of provider and parent, parent race and income, severity of child illness and duration in treatment) impacts effect size estimates by adding interaction terms to models and estimating effect sizes separately for different levels of the covariate (e.g. male and female for parent gender). *Missing Data:* We will compare baseline variables between subjects who drop out of the study to those who do not using two-sample *t* tests, chi-square tests or their non-parametric equivalents as appropriate. If we find that the missing data appear to be MNAR, this information will be used in designing the larger trial. Because of the relatively small sample size, we will not attempt to model the missing data mechanism in this pilot study. *Sex as a biological variable:* As noted above, we will estimate effect sizes by sex for all outcomes. [name] will lead the qualitative analysis of the semi-structured interviews with input from PI and research team. The interviews will be coded with standard content analytic procedures.

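### Provider T2 follows workshop completion and no T2 is planned after early stopping, so the provider pre/post change is in effect a completers-only estimate and the intent-to-treat statement is unsupported

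*Protocol*

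**What the plan says.** **Providers.** Protocol section 5.0 (Study Duration/Timeline) has providers take a workshop of at most 4.5 hours on a learning platform over 2-3 weeks, and then: "After the provider completes the workshop, he/she will be contacted by study staff to complete the post-intervention measures (T2"). Section 6.0 (Data collection) says that staff "will schedule a follow-up assessment 1- 4 weeks post intervention training (T2"). The Compensation paragraph pays providers outside two named centers $100 for a package of T1, workshop, T2 and interview.

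**Parents.** The parent component is flexible: "It will include up to three 60 minutes sessions (the third session is optional"). On assessments, the Data collection text says: "Parents will be contacted and asked to schedule a convenient time to complete the surveys with the study staff". Parents are paid for each assessment and, separately, for each session. The study schema places Time 2 after the sessions.

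**Withdrawal.** The Safety text in section 7.0 says that a participant may contact the PI to withdraw formally, "or he/she may simply choose to stop coming to the study sessions". It continues: "If the participant chooses to withdraw, a study representative will call the participant to make sure he/she is ok". Contact numbers for other resources are also offered. No outcome assessment is mentioned. Section 8.0 adds nothing on this.

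**Analysis.** Section 9.0 states "Analyses will be intent-to-treat". It uses the T2 value as the outcome, compares dropouts with others at baseline only, and declines to model the missing-data mechanism. The SAP says that the analysis was changed because the design became pre/post. It tests change scores for the two provider groups, reports no parent tests because only 3 parents had both assessments, and does not mention intent-to-treat.

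**The concern.** An intent-to-treat estimate needs outcomes from people who stop the intervention as well as from those who finish it. Here the provider T2 contact is triggered by finishing, the T2 window is counted from the training, and nothing is arranged for a provider who leaves the course part-way. The selection thus arises in data collection. A later analysis could cover everyone enrolled only by making untestable assumptions about scores that were not requested, and the protocol says it will not model the missing data.

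This matters because the pilot is meant to supply effect sizes for a larger randomized trial. Providers who find the workshop burdensome or unhelpful are plausibly those who stop. With a single group and no concurrent control, no second arm with similar attrition offsets the selection.

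**Working it through.** **1. The plan's own figure.** Inputs from Sample size justification: 80% power, two-sided alpha 0.05, pre/post correlation 0.5, intraclass correlation 0.05, 40 parents recruited, 20% dropout. I assume two equal groups and 5 parents per provider, falling to 4 after dropout; the size of the historical control is not given.
- Retained per group: 40 x 0.8 = 32.
- Baseline-adjustment factor: 1 - 0.5² = 0.75.
- Design effect: 1 + (4 - 1) x 0.05 = 1.15.
- Detectable effect: 2.80 x sqrt(0.75 x 1.15 x 2/32) = 0.650; power at 0.65 is 79.9%.

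The stated 0.65 reproduces and is not in error. It rests on the 32 retained with T2, not the 40 enrolled. It concerns parents in a two-group comparison, so it says nothing about providers.

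**2. A provider who stops part-way.** The T2 contact follows completion, so it is not triggered. The window runs from the training, so there is no clear date to count from. The $100 package, where it applies, includes the workshop, so as written it cannot be earned by giving T2 alone. If the provider is regarded as withdrawn, what follows is a welfare call and resource numbers. No other text asks this provider for T2.

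**3. A parent who stops after one session.** Scheduling of the surveys carries no completion condition, and each assessment is paid for whether or not sessions were attended. Nothing prevents T2, but nothing says when or whether it is sought. The rule is absent rather than restrictive.

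**4. What the analyses do without T2.** In the section 9.0 model a person without T2 contributes no outcome. In the SAP, change is post minus pre, so a person without T2 has no change score. Both are complete-case.

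**5. Size, as an illustration.** Let p be the share not completing, dC the mean change in completers and d0 the mean change in non-completers.
- All-enrolled effect = (1 - p) x dC + p x d0.
- Completers-only estimate minus all-enrolled effect = p x (dC - d0).

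All values are assumed; p = 0.20 is borrowed from the protocol's parent dropout figure. With dC = 0.50:
- p = 0.20, d0 = 0: 0.8 x 0.50 = 0.40; gap 0.10 SD, ratio 0.50/0.40 = 1.25.
- p = 0.20, d0 = 0.25: 0.40 + 0.05 = 0.45; gap 0.05 SD.
- p = 0.20, d0 = 0.50: 0.50; no gap.
- d0 = 0 and p = 0.10, 0.30 or 0.50: 0.45, 0.35 or 0.25; gap 0.05, 0.15 or 0.25 SD.

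With dC = 0.65, p = 0.20 and d0 = 0, the gap is 0.20 x 0.65 = 0.13 SD.

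**The case against.** The strongest reply is that the intent-to-treat sentence belongs to a two-group analysis that the SAP has replaced, and that the SAP makes no such promise. This stands in part. The conflict lies within the protocol, whose section 9.0 still carries the sentence. The SAP's own analysis remains limited to people with both assessments and does not say so in those terms.

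A second reply is that this is a feasibility pilot with exploratory testing, which logs "attrition rate, reasons for missed session or intervention completion; and (3) measurement completion rates" and compares dropouts with others at baseline. That makes selection visible, but it does not supply the missing T2 scores.

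Several stronger readings are tempting, and the documents do not support them:
- *People who stop never get T2.* No text forbids it. The explicit completion trigger covers providers only, and for parents the inference would rest on silence.
- *Missing sessions counts as leaving the study.* The sentence in section 7.0 is permissive, refers to study sessions, and concerns how a person who wishes to withdraw may do so. A parent who skips the optional third session has not stopped.
- *An all-enrolled effect cannot be estimated.* It could be, under untestable missing-data assumptions; the protocol declines to make them.
- *Medical-record outcomes are lost too.* Retention is counted over 6 months from baseline and access to administrative data follows parent consent. Neither depends on attendance.
- *About a fifth of the 16 providers will lack T2.* The 20% is a parent figure; no provider dropout rate is given.
- *The 3 parents with paired data show this rule at work.* The SAP gives neither a reason nor the number enrolled.

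**Conclusion.** The point holds for providers. As written, T2 is sought after workshop completion and no T2 is arranged after early stopping, so the provider pre/post change is in effect a completers-only estimate and the intent-to-treat statement in section 9.0 has no procedure behind it. For parents, the defect is only that T2 after stopping is not addressed. The documents give no separate T2 procedure for the second provider group in the SAP; I assume that it follows the same one.

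The size of any bias is unknown. It equals the share not completing times the difference in change between completers and non-completers, and neither quantity is given for providers. The illustration of 0.50 against 0.40 rests wholly on assumed values, and the bias vanishes if non-completers change equally. A reader might infer that the reported effects are certainly too favourable; the documents support only that they may be. This is a cheap improvement worth making, and it does not invalidate the pilot.

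**What to change.** **If data are still being collected.** In Study Duration/Timeline, Data collection and the withdrawal text of section 7.0:
- Separate stopping the training from withdrawing from follow-up.
- Date T2 from T1, or from the scheduled end of training, with a fixed window for everyone with a T1. The present width of 1 to 4 weeks could be kept if it is counted from the scheduled end.
- Seek T2 from non-completers in the same way as from completers, for example at the call already planned after withdrawal.

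**If collection is finished**, as the past tense of the SAP suggests: replace intent-to-treat with complete-case in describing the analysis, report how many enrolled providers and parents lack T2 and why, and carry the T2 rule into the larger trial.

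**Cost.** Changes to protocol wording, and to consent wording if needed, plus a few extra contacts and surveys. Some T2 forms will come from people with little exposure, and the estimate will probably be smaller. The complete-case route costs only wording and a count.
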